Treatment with a CGRP-neutralizing antibody, galcanezumab in this specific patient group, being seen in the PI's clinics on a regular basis, is rooted in the rationale of unmistakable presence of clinical signs of neurogenic inflammation in the painful territory, such as episodic swelling combined with redness/hyperemia, also relief by external cold application which typically patients with trigeminal or glossopharyngeal nerve pain abhor.

Primary Outcome Measures

Primary criterion is to establish an excellent safety profile that recapitulates the favorable data recorded in migraineurs. The primary pain-related objective is reduction of pain and reduced use of rescue and other anti-pain medication.

Inclusion Criteria

- G50.1 diagnosis (can encompass an add-on G50.0 and other headache G43.... codes), or G52.1 diagnosis code (with explicit mentioning of pain of glossopharyngeal origin) **AND** small fiber neuropathy diagnostic codes G63.3, G60.8, G62.8 (can encompass fibromyalgia diagnostic code M79.7)
- 18-80 years old
- not allergic to galcanezumab and other hu mAb biologics

Exclusion Criteria

- allergic to galcanezumab and other hu mAb biologics
- pregnancy

Study Design / Overview

We propose to treat patients open label for 12 weeks, with galcanezumab, supplied by Eli Lilly, as add-on to all other therapeutic measures. We propose to use a 240mg/120mg/120mg regime, with subcutaneous (self-)injections every 4 weeks.

To reflect pain experienced by patients, the primary read-out is pain level on a 0-10 visual analog scale. We will be prompting patients to record a daily summary read at the end of each day.

[figure not shown]
The second criterion is reduction of intake of anti-pain medication (rescue PRN or regular) which the patients will record.

Chronic pain, especially fibromyalgia pain combined with trigeminal or glossopharyngeal nerve pain, is a potent disruptor of circadian rhythm. We strongly believe that this is an important and hitherto under-appreciated contributor to individual disease burden. Therefore, the third criterion is assessment of circadian rhythm function. We will assess this by having the patient rate subjectively how energetic they feel during awake day-time. Wearable activity monitors will be used to address how many hours patients sleep per

24h period, with detailed focus on total duration of sleep/rest and duration of night-time sleep only.

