Before treatment, there will be a 4 week observation-only period, and another one 8 weeks post-treatment, so that the total study period will be 6 months.

We aim for 20 patients to be included in this study.

see more detailed graphics in the next section

In terms of ancillary, laboratory-based studies, we intend to draw blood before treatment and at the 45-, 75-, 105- and 135-day of treatment time-points. We will measure cytokine/chemokine/lipid pain- and inflammation markers in patients' serum, also determine microRNA in their serum, and genomic DNA polymorphisms, the latter only at baseline. Please see next section for more detail.

To establish safety of the anti-CGRP treatment in this patient cohort, blood draw at baseline and at the 45-, 75-, 105- and 135-days of treatment time-points will also include routine systemic sentinel/surveillance markers, namely comprehensive metabolic panel and complete blood count with differential, and complete urinalysis. No more than 45 ml of blood will be collected at any given visit.

In terms of additional safety parameters, we propose an open, patient-kept side-effect log, plus home-based recordings of blood pressure, heart rate and weight at a frequency of 2x/week.

We will set up a data and safety monitoring board for proper management and oversight of data handling and patient safety-related issue; see next section.

[figure not shown]
We expect to observe effective treatment, at least in a significant subgroup of patients. Effectiveness of treatment, also magnitude of any observed therapeutic effect will be correlated with the pain/inflammation proteinaceous, lipid and RNA-based biomarkers in patients' serum, also with any polymorphisms in the patients' genomic DNA.

We also expect galcanezumab treatment to show another record of safe treatment, our expectation sculpted by analysis of in-depth data from treatment of migraineurs. Yet we will remain vigilant and implement the proposed safety sentinel measures in order not to miss adverse effects. This appears prudent because trigeminal or glossopharyngeal nerve pain plus small-fiber neuropathy is a different underlying disorder than migraine, likely representing a higher prevalence in peri-menopausal female patients. We also believe it is likely that level of chronic pain suffering-associated stress will be higher in our study population than in migraineurs.

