[name] will be the Principal Investigator. He has the primary responsibility for ensuring the ethical conduct of this research study. This includes protecting human subjects' rights, safety and welfare, protocol compliance, and adherence to institutional, state and federal regulations and guidance, and for proper communication with the financial support source. He is responsible for ensuring informed consent is appropriately obtained from each participant and for appropriately maintaining study records. He is also responsible for complying with the financial and administrative policies and regulations associated with the award, overall fiscal management of the project, and conflict of interest disclosure. He will oversee all aspects of this trial, but some tasks can be delegated to other research team members. He will be responsible for ensuring that all research team members have appropriate education, training and qualifications to assume delegated study tests. All study team members are responsible for ensuring that the conduct of the study is compliant with institutional, state and federal regulations.

[name] and [name] will serve as sub-investigators.

Data entry and management will rely on a RedCap database that will be set up specifically for this study. The Research Coordinator/Research Nurse will be provided by Duke's Neurology Clinical Research Unit at [name].

7) Risks and Adverse Reactions – Adverse Event (AE) management

Investigators are responsible for monitoring the safety of subjects who have entered this study and for alerting the Duke University IRB to any event that seems unusual, even if this event may be considered an unanticipated benefit to the subject. The PI is responsible for the appropriate medical care of subjects during the study.

Investigators must document their review of each safety report.

The PI remains responsible for following, through an appropriate health care option, AEs that are serious or otherwise medically important, considered related to galcanezumab or the study, or that caused the patients to discontinue galcanezumab before completing the study. The patient should be followed until the event resolves, stabilizes with appropriate diagnostic evaluation, or is reasonably explained.

The frequency of follow-up evaluations of the AE is left to the discretion of the PI.

Lack of drug effect is not an AE.

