After the informed consent form (ICF) is signed, study site personnel will record via case report form (CRF) the occurrence and nature of each subject's preexisting conditions, including clinically significant signs and symptoms of the pain condition under treatment in this study. In addition, site personnel will record any new conditions as AEs. Investigators should record their assessment of the potential relatedness of each AE to galcanezumab and/or protocol procedure via CRF.

The PI will interpret and document whether or not an AE has a reasonable possibility of being related to galcanezumab, its injection, or a study procedure, taking into account the disease, co-morbid conditions, concomitant treatment or pathologies.

A “reasonable possibility” means that there is a cause and effect relationship between galcanezumab, and/or study procedure and the AE.

The PI answers “yes/no” when making this assessment.

Planned surgeries and nonsurgical interventions should not be reported as AEs unless the underlying medical condition has worsened during the course of the study.

If galcanezumab is discontinued for a given patient as a result of an AE, study site personnel must report this to the Duke IRB via CRF, clarifying if possible, the circumstances leading to discontinuations of treatment.

A severe AE (SAE) is any AE from this study that results in one of the following outcomes:

- death
- initial or prolonged inpatient hospitalization
- a life-threatening experience (that is, immediate risk of dying)
- persistent or significant disability/incapacity
- congenital anomaly/birth defect
- important medical events that may not be immediately life-threatening or result in death or hospitalization but may jeopardize the patient or may require intervention to prevent one of the other outcomes listed in the definition above. Examples of such medical events include allergic bronchospasm requiring intensive treatment in an emergency room or at home, blood dyscrasias or convulsions that do not result in inpatient hospitalization, or the development of drug dependency or drug abuse.

All AEs occurring after signing the ICF are recorded in the CRF and assessed for fulfilling criteria of SAE. SAE reports are forwarded to the Duke University IRB. For each SAE, the Duke University IRB safety commission will decide within 48h whether the case will be forwarded to Eli Lilly immediately.

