Study site personnel must alert the Duke IRB of any SAE within 24 hours of PI or any other member of the clinical team becoming aware of the event.

If alerts are issued via telephone, they are to be immediately followed with official notification on study-specific SAE forms. This 24-hour notification requirement refers to the initial SAE information and all follow-up SAE information.

Pregnancy does not meet the definition of an AE. However, to fulfill regulatory requirements any pregnancy should be reported following the SAE process to collect data on the outcome for both mother and fetus.

Investigators are not obligated to actively seek AEs or SAEs in subjects once they have completed the 90-day treatment period. However, if the investigator learns of any SAE, including a death, during the 60 day observational period, the PI must promptly notify the Duke IRB. This will also apply to an SAE after finishing the study if the PI considers the event reasonably possibly related to treatment with galcanezumab or study participation.

Suspected unexpected serious adverse reactions (SUSARs) are serious events that the investigator identifies as related to galcanezumab or procedure. United States 21 CFR 312.32 and European Union Clinical Trial Directive 2001/20/EC and the associated detailed guidances or national regulatory requirements in participating countries require the reporting of SUSARs. The Duke IRB has procedures that will be followed for the identification, recording and expedited reporting of SUSARs that are consistent with

global regulations and the associated detailed guidances.

Enrolled patients will be instructed to contact the PI and his study team as soon as possible if the patient has a complaint or problem with galcanezumab so that the situation can be assessed.

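### The duty to ask about adverse events ends with the 90-day treatment period, so capture in the 60-day observation may be less complete, although safety is the primary criterion

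*Combined protocol and SAP*

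**What the plan says.** Section 7 (Risks and Adverse Reactions – AE management) contains both a general duty and a specific exemption.

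- General duty: "Investigators are responsible for monitoring the safety of subjects who have entered this study", and "All AEs occurring after signing the ICF are recorded in the CRF and assessed for fulfilling criteria of SAE". Neither sentence has an end date.
- Exemption: "Investigators are not obligated to actively seek AEs or SAEs in subjects once they have completed the 90-day treatment period".
- Rule for the observation period: "if the investigator learns of any SAE, including a death, during the 60 day observational period, the PI must promptly notify the Duke IRB". Nothing comparable is said there about non-serious AEs.

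Primary Outcome Measures gives safety first place: "Primary criterion is to establish an excellent safety profile that recapitulates the favorable data recorded in migraineurs". Study Design / Overview says that the team will "implement the proposed safety sentinel measures in order not to miss adverse effects", because this population differs from migraineurs. It lists the tools: "we propose an open, patient-kept side-effect log, plus home-based recordings of blood pressure, heart rate and weight", and laboratory safety tests with "blood draw at baseline and at the 45-, 75-, 105- and 135-days of treatment time-points". Section 4 (patient equipment) describes a daily booklet that includes a page for day 180.

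**The concern.** The exemption begins inside the study. Study Design / Overview counts the post-treatment observation as part of the six-month study period, and section 7 treats events after the end of the study as a separate, later case. Section 11 (Brief Statistical Analysis Plan) also uses the observation period as a comparison period for pain. Pain is thus to be recorded daily to the end, while staff need no longer enquire about the outcome that the protocol ranks first.

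If AEs are asked about on treatment and mostly volunteered afterwards, the two periods are not observed in the same way. A lower AE count in observation could then reflect less asking rather than fewer events. DSMB review of accumulating adverse events (section 3) and the planned correlation of markers with safety metrics (section 11) both depend on what is captured.

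**Working it through.** **Inputs.** Treatment 90 days, observation 60 days and run-in 30 days (section 11). Weekly version: 12, 8 and 4 weeks, that is 84, 56 and 28 days (Study Design / Overview). Three injections at 4-week intervals (same section). Safety draws at days 45, 75, 105 and 135. Target of 20 completers (section 11). I assume that the treatment period starts at the first injection.

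**1. The plan's own figure.** The stated total is 6 months. In days, 30 + 90 + 60 = 180, which agrees with that total and with the day-180 booklet page. In weeks, 28 + 84 + 56 = 168 days, somewhat shorter.

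**2. Share of time after first dose with no duty to ask.** Observation / (treatment + observation):
- days: 60 / (90 + 60) = 60/150 = 40%
- weeks: 56 / (84 + 56) = 56/140 = 40%

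For 20 completers this is 20 × 60 = 1,200 of 20 × 150 = 3,000 patient-days (weekly version: 1,120 of 2,800).

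**3. Asking that already follows the last injection.** Injections fall at about days 0, 28 and 56. The duty to ask then runs for a further 90 − 56 = 34 days, or 84 − 56 = 28 days in the weekly version. That is at least one dosing interval.

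**4. Safety draws inside the observation window.** The documents leave open whether draw days count from first dose or from the start of the run-in.
- From first dose, which is the more literal reading: days 105 and 135 both fall after treatment. The last is observation day 135 − 90 = 45 of 60 (weekly: 135 − 84 = 51 of 56).
- As study days: treatment ends at 30 + 90 = 120, so only day 135 qualifies, at observation day 15 of 60 (weekly: 135 − 28 − 84 = 23 of 56).

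Under either count, at least one existing contact falls in the window.

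**5. The rules side by side.** The recording rule covers every AE after consent. The exemption removes the step by which many AEs become known. A known late AE must still be recorded, but nobody has to find out whether there was one. The two sentences can be read together, but only by accepting that recording in observation depends on what reaches the team unprompted.

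**The case against.** The strongest reply is that seeking is not recording. Section 7 lifts a duty to ask; it neither forbids asking nor ends CRF recording. The named safety tools have no stated stop at day 90: the side-effect log, the twice-weekly home vital signs and one or two safety draws. Patients are told to contact the team about problems. Serious, medically important or related AEs, and those that led to discontinuation, are followed until they resolve or stabilise. Asking already extends about a month past the third injection. The exposed gap is therefore mainly new-onset, non-serious AEs that are neither logged nor volunteered, plus any SAE that never reaches the team.

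Most of this stands, and it limits the consequence. It does not remove it. The text does not say when staff review the log or that its entries become CRF adverse events. The instruction to call concerns problems with galcanezumab, and a patient no longer on the drug may not connect a new condition with it. Laboratory tests and vital signs do not capture most symptoms. Follow-up to resolution applies only to AEs already known.

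Three stronger readings are tempting and are not supported:
- **Safety data stop at day 90.** They do not, for the reasons above.
- **40% of AEs would be lost.** That would need a constant AE rate and no capture at all in observation. The documents give no AE rate and do provide for some capture.
- **A zero-event risk limit for 20 patients is undermined.** The plan makes no such claim and sets out no period-specific AE rate.

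The schedule of activities could not be read in the text available. If it lists AE questioning at post-treatment visits, the practical effect shrinks to a matter of wording, but the express exemption would still need to be reconciled with it.

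**Conclusion.** The concern holds in a limited form. The exemption is a stated rule rather than a missing detail, and it fits poorly with a primary safety criterion and with the open-ended recording rule in the same section. Followed as written, it may make capture of new-onset AEs, mainly non-serious ones, less complete in observation than on treatment.

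The only size the documents support is the 40% of post-first-dose time without a duty to ask, which is the same in the day and week versions. The loss of events is partial, and its amount cannot be derived from the documents. The conclusion assumes that staff apply the specific follow-up sentence rather than the general duty, and that the schedule of activities does not already require AE questioning after treatment.

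**What to change.** Amend the exemption in section 7 so that it agrees with the recording rule there: AE and SAE enquiry and CRF recording continue to the end of the 60-day observation. Carry this out at contacts that already take place, namely the post-treatment safety draw or draws and the final data acquisition. State that the side-effect log is reviewed at each of these contacts.

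The cost is an amendment to one sentence of a safety section, a short line on log review, a little more coordinator time and a somewhat higher reported AE count. An extra telephone call at the end of observation, or AE tables by period with days at risk, would be optional additions; the repair does not depend on them.

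### The patient contact instruction and log are worded around galcanezumab, narrower than the protocol's own AE definition, so events patients do not link to the drug may be reported late, or missed in the 60-day follow-up

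*Combined protocol and SAP*

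**What the plan says.** The Primary Outcome Measures section puts safety first: "Primary criterion is to establish an excellent safety profile that recapitulates the favorable data recorded in migraineurs".

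Section 7 (Risks and Adverse Reactions) sets a definition that does not depend on cause. Besides pre-existing conditions, "site personnel will record any new conditions as AEs", and "All AEs occurring after signing the ICF are recorded in the CRF and assessed for fulfilling criteria of SAE". Causality is assigned to the investigator: "The PI will interpret and document whether or not an AE has a reasonable possibility of being related to galcanezumab".

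The patient-facing wording is different. Later in Section 7, enrolled patients are to contact the PI and team "as soon as possible if the patient has a complaint or problem with galcanezumab so that the situation can be assessed". In the Study Design / Overview section the patient's own safety record is described thus: "we propose an open, patient-kept side-effect log".

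Section 7 also ends the duty to look actively for AEs and SAEs when the 90-day treatment period ends. For the 60-day observation period it requires prompt IRB notification of an SAE if the investigator comes to know of one.

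**The concern.** Site staff can record only what they learn of. Between visits, what they learn of depends largely on what patients have been asked to report. A hospital stay for infection, a cardiovascular event or an accident is an AE or SAE under Section 7, but a patient who sees no link to the injection could reasonably think that the contact instruction does not apply. The same holds for pregnancy, which Section 7 wants reported through the SAE process although it is not plainly a problem with the drug.

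This matters because safety is the primary criterion, and because the overview itself urges vigilance on the ground that the condition differs from migraine. A reaction nobody expects is one that a patient is unlikely to attribute to the drug. Two oversight steps also depend on timely reports: the 24-hour SAE notification runs from the team's awareness, and extra DSMB meetings (Section 3) are triggered by AE frequency.

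**Working it through.** The plan states no figure for AE capture, so there is none to reproduce. The check is mainly a comparison of passages.

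**1. Scope of the rules (Section 7; overview).**
- AE definition: any new condition after consent, whatever its cause.
- Who judges cause: the PI.
- Prompt-contact instruction: a complaint or problem with galcanezumab.
- Patient log: side effects.

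The last two are narrower than the first and place a causal filter with the patient that the second gives to the PI.

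**2. Other routes during treatment.** These are the all-AE recording rule, home vital signs twice a week, scheduled laboratory panels and urinalysis, and the daily list of all medications (Section 4). Active AE seeking is also implied, since it is waived only afterwards. An event the patient does not attribute to the drug can therefore still be found, but the readable text does not say how or how often AEs are asked about, or when the log is read. The supported consequence is possible delay.

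**3. Routes in the 60-day observation period.** Active seeking is waived. The booklet has 200 daily pages, so the diary can continue, and home measurements are logged on its pages. These show drugs taken and measured values. They do not directly show an outside admission, and the booklet content listed in Section 4 has no AE field. The supported consequence is that an event may be missed.

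**4. Can a delay in days be stated?** Blood draws are at days 45, 75, 105 and 135, described as days of treatment. The gaps are 45 − 0 = 45, then 75 − 45 = 105 − 75 = 135 − 105 = 30 days. Section 11 gives a 30-day run-in, 90-day treatment and 60-day observation.
- Read as treatment days: observation runs from day 90 to day 90 + 60 = 150. The draws at 105 and 135 fall within it, and the last gap is 150 − 135 = 15 days.
- Read as study days: treatment runs from about day 30 to day 120 and observation to day 180. The first draw is 45 − 30 = 15 days after the first dose, only the day-135 draw falls in observation, and the last gap is 180 − 135 = 45 days.

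The two readings give different gaps, and nothing says that draws are the only contacts or that AEs are asked about there. No single delay follows.

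**5. For scale only.** With 20 completers, one patient is 1/20 = 5 percentage points of any observed rate. Let p be an assumed true event risk per patient and c an assumed share of events captured. The chance of recording at least one event is 1 − (1 − pc)^20.

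| p | c = 100% | c = 75% | c = 50% |
|---|---|---|---|
| 5% | 64.2% | 53.4% | 39.7% |
| 10% | 87.8% | 79.0% | 64.2% |
| 20% | 98.8% | 96.1% | 87.8% |

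For example, 1 − (1 − 0.10 × 0.50)^20 = 1 − 0.95^20 = 64.2%. Both p and c are assumptions. The table shows how sensitive a 20-patient safety record would be to incomplete capture, not that capture is incomplete.

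**The case against.** The strongest reply is that the contact sentence does not define AE collection. It does not say that patients should call about nothing else, and it can be read as a help line for a self-injected product. The record itself rests on rules free of attribution, supported by what the overview describes: "we propose an open, patient-kept side-effect log, plus home-based recordings of blood pressure, heart rate and weight at a frequency of 2x/week". The log is called open, side effect is ordinary lay language, and nothing tells patients to establish cause before writing. The medication diary would show treatment for an infection whatever the patient believed. The schedule of activities and consent pages are not visible and may hold AE review points or a broader instruction.

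Most of this stands, and it rules out stronger readings that a reader might infer:
- *That unattributed events never reach the record.* During treatment the other routes contradict this.
- *That the final AE count will be pulled towards the migraine profile.* Delay alone does not lower a count, and no document shows that events are lost.
- *That reports would be 30 to 45 days late.* This treats blood draws as the only contacts and depends on which day count is used.
- *That a given share of events, such as half, falls outside the instruction.* The documents give no attribution share, and such a share would describe one contact route, not the whole AE record.

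The reply does not remove the mismatch between the AE definition and the patient wording, nor does it cover the observation period, where Section 7 itself withdraws active seeking.

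**Conclusion.** The concern holds in a limited form. The only prompt-contact instruction in the readable text, and the title of the patient log, are narrower than the AE definition in Section 7. During treatment the likely effect is later reporting of events that patients do not blame on galcanezumab. In the 60-day observation period such events may be missed.

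The size cannot be estimated from the documents. The conclusion assumes that at least some patients take the wording at face value and that the pages not shown contain no broader instruction. If they do contain one, what remains is to bring Section 7 into line with it. The change is worth making because safety is the primary criterion and the remedy is small.

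**What to change.** Replace the contact sentence in Section 7 with wording such as: *Patients are instructed to contact the study team as soon as possible about any new or worsened health problem, emergency visit, hospital admission or pregnancy, whether or not they think it is due to galcanezumab, until the end of the post-treatment observation period. Relatedness is judged by the PI as set out in this section.* Head the patient-kept log *Any health problem*, and carry the same wording into the patient instructions.

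The cost is one sentence, one log heading and a few more calls. More unrelated AEs will be recorded, so the crude AE rate will look slightly less favourable; the PI's relatedness assessment allows related events to be shown separately. No treatment rule changes.
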